Appendix 3. Pooled Cohort Risk and Score Calculation

No.	Parameters	Coefficient			
		Female		Male	
		White or Other	African America	White or Other	African America
1	ln Age (y)	-29.799	17.114	12.344	2.469
2	ln Age, Squared	4.884	N/A	N/A	N/A
3	ln Total Cholesterol (mg/dL)	13.540	0.940	11.853	0.302
4	ln Age × ln Total Cholesterol	-3.114	N/A	-2.664	N/A
5	ln HDL Cholesterol (mg/dL)	-13.578	-18.920	-7.990	-0.307
6	ln Age × ln HDL Cholesterol	3.149	4.475	1.769	N/A
7	ln Treated Systolic BP	2.019	29.291	1.797	1.916
8	ln Age × ln Treated Systolic BP	N/A	-6.432	N/A	N/A
9	ln Untreated Systolic BP	1.957	27.820	1.764	1.809
10	ln Age × ln Untreated Systolic BP	N/A	-6.087	N/A	N/A
11	Current Smoker (1=Yes, 0=No)	7.574	0.691	7.837	0.549
12	ln Age × Current Smoker	-1.665	N/A	-1.795	N/A
13	Diabetes (1=Yes, 0=No)	0.661	0.874	0.658	0.645
A	Baseline Survival	0.9665	0.9533	0.9144	0.8954
B	Individual Sum = $\sum(\text{coefficient} \times \text{parameter})$	For each individual patient, individual sum is summation of product of each parameter and its corresponding coefficient for that sex-race group for all parameters listed above (#1 - #13). Note: N/A indicates that the specific coefficient is not available thus the corresponding parameter will not be included in calculation.			
C	Population Mean	-29.18	86.61	61.18	19.54
D	Pooled Cohort SCORE	= B - C = Individual Sum - Population Mean			
E	Pooled Cohort Risk = Estimated probability of a first hard ASCVD* event within 10 years	= $1 - A \wedge \exp(B-C)$ = $1 - \text{Baseline Survival} \wedge \exp(\text{Individual Sum} - \text{Population Mean})$			

* ASCVD = atherosclerotic cardiovascular disease; BP = blood pressure; Ln = natural logarithm.

- Age is the actual age when the laboratory parameters are collected for the visit. Smoker is collected at Screening/Baseline of the Randomized Phase.
- If a subject had diabetes at baseline, the diabetic status will be yes for all the postbaseline visits. If the subject does not have diabetes at baseline, the diabetic status will be determined based on the AE start date. If the AE start date is on or prior to the laboratory date of a specific visit, then the diabetic status will be yes for that visit and later visits. If the day of the AE start date is missing, it will be imputed using the 1st day of the month.
- Treatment status of hypertensives will be determined by the usage of anti-hypertensive medications on the dates when blood pressures are collected. Anti-hypertensive medication with a start date prior to or on the date of blood pressures taken and a stop date on or after it. Systolic BP will be considered as treated Systolic BP.
- Total Cholesterol and HDL Cholesterol need to be measured from the same blood draw. Systolic BP record closest to the date when Total Cholesterol and HDL Cholesterol are measured will be used for the risk and score calculation.
- Round Pooled Cohort Risk Score to 0.001.

Appendix 4. Liver Function Prognostic Scores

- **Child-Pugh Score Calculation**

	1	2	3
HE	None No encephalopathy and not on any treatment for hepatic encephalopathy	Medication-Controlled Subject is lethargic, may have moderate confusion Subject is receiving medical therapy for HE	Medication-Refractory Marked confusion/incoherent, rousable but sleeping or comatose
Ascites	None No ascites and not on treatment for ascites	Mild/Moderate Cross sectional imaging showing ascites Abdominal distension Medication for ascites	Severe (diuretic-refractory) Visible clinically
Total Bilirubin (mg/dL)	< 2	2-3	> 3
Albumin (g/dL)	> 3.5	2.8-3.5	< 2.8
INR	< 1.7	1.7-2.3	> 2.3

There are 5 components for CP score as seen in the first column. Each will be assigned a subscore ranging between 1 and 3 based on the matching condition as described in the corresponding row and the value in the header row of the corresponding column. For example, when total bilirubin value is 2.5 mg/dL, the total bilirubin subscore will be 2.

CP score is obtained by adding the subscore for each parameter, ranging between 5 and 15.

For Screening, HE and ascites closest to laboratory collection date will be used; for Day 1 and postbaseline visits, HE and ascites will be from the same day as laboratory data collected. If baseline CP score is missing due to unevaluable laboratory data, baseline CP score will be calculated using the last laboratory values collected prior to (OL) Day 1.

- **MELD Score Calculation**

MELD score = 3.78 [Ln total bilirubin (mg/dL)] + 11.2 [Ln INR] + 9.57 [Ln serum creatinine (mg/dL)] + 6.43. If the serum creatinine, the total bilirubin or the INR value is < 1.00 mg/dL, the calculation will use 1.00 as the test value. If the serum creatinine is > 4.00 mg/dL or subjects on dialysis, the calculation will use 4.00 as the serum creatinine value.

Appendix 5. Health Related QoL Score Calculation

• SF-36

Scoring of the SF-36 scales will be performed as described in Chapter 6 of the SF-36 Health Survey Manual and Interpretation Guide, Version 2. Summary will be done for 8 domains of the SF-36 (physical functioning, role-physical, bodily pain, general health, vitality, social functioning, role-emotional, and mental health), and for the physical component score and mental component summary.

• CLDQ-NAFLD

CLDQ-NAFLD scores are calculated using subject responses to 36 questions in the questionnaire. If R_i is the score for the patient's response to the item i , for $i=1, 2, \dots, 36$ then the 6 domain scores are calculated as follows:

— Abdominal = Mean of {R1, R5, R17}

— Fatigue = Mean of {R2, R4, R8, R11, R13, R35}

— Systemic = Mean of {R3, R6, R21, R23, R27, R36}

— Activity = Mean of {R7, R9, R14, R30, R31}

— Emotion = Mean of {R10, R12, R15, R16, R19, R20, R24, R26, R34}

— Worry = Mean of {R18, R22, R25, R28, R29, R32, R33}

Here “Mean” is the average of nonmissing items (SAS mean function). Each score is calculated only if at least half of corresponding items are not missing. Otherwise, the score will be missing.

Overall CLDQ score is calculated by taking the mean of 6 domain scores {abdominal, fatigue, systemic, activity, emotion, worry}. Overall CLDQ score will be summarized.

• WPAI: NASH

The response to Question 1 of this questionnaire provides the binary endpoint whether or not the subject had been in a paid employment during the week prior to assessment.

If the subject had been in a paid employment (Response to Q1 is “Yes”) at the visit when questionnaire was given, then following three scores are derived:

- Percent work time missed = $100 \times Q2 / (Q2 + Q4)$
- Percent impairment while working = $100 \times Q5 / 10$

- Percent overall work impairment =

$$100 \times \left[\frac{Q2}{(Q2 + Q4)} + \left(1 - \frac{Q2}{Q2 + Q4} \right) \times \frac{Q5}{10} \right]$$

Question 6 is applicable to all subjects:

- Percent activity impairment = $100 \times Q6 / 10$.
- Percent overall work impairment and percent activity impairment will be summarized.

- **EQ-5D**

Scoring of EQ-5D will be performed as described in EQ-5D-5L user guide. Summary will be done for 5 dimensions in descriptive system (mobility, self-care, usual activities, pain/discomfort and anxiety/depression) and the EQ Visual Analogue Scale.

- **HRUQ**

The number of visits/days for the following questions will be summarized.

- Outpatient non-emergent clinic visits (number of visits)
- Outpatient non-emergent clinic visits related to disease (number of visits)
- Outpatient emergent department visits (number of visits)
- Outpatient emergent department visits related to disease (number of visits)
- Outpatient surgeries and procedures (number of visits)
- Outpatient surgeries and procedures related to disease (number of visits)
- Inpatient surgeries and procedures (number of visits)
- Inpatient surgeries and procedures related to disease (number of visits)
- Number of days hospitalized (number of days)
- Number of days hospitalized related to disease (number of days)

Appendix 6. NAFLD Activity Score (NAS) and Steatosis, Activity, and Fibrosis (SAF) Score Calculation

NAS score is calculated as the sum of steatosis, lobular inflammation and hepatocellular ballooning. SAF score is calculated as the sum of steatosis (same as NAS calculation), activity and fibrosis (according to the NASH CRN classification) subscores. Activity subscore is defined as sum of lobular inflammation and hepatocellular ballooning, where both grade 2 and 3 of lobular inflammation will be treated as 2.

Appendix 7. Noninvasive markers for Fibrosis

- **Enhanced Liver Fibrosis (ELF)**

ELF test score = $2.278 + 0.851 \times \ln(\text{hyaluronic acid}) + 0.751 \times \ln(\text{PIIINP}) + 0.394 \times \ln(\text{TIMP1})$;

Note: All ELF test score components (hyaluronic acid, PIIINP and TIMP1) need to be measured from the same blood draw. ELF test score will only be calculated when ELF test score is missing and components are less than the LOQ or above the upper LOQ. Individual components are to be imputed per data handling conventions in Section 3.7, and ELF test score will be calculated based on the imputed values of components.

- **Fibrosis-4 (FIB-4) Index Calculation:**

FIB-4 Index = $\text{round}((\text{age} \times \text{AST}) / (\text{platelet} \times \text{sqrt}(\text{ALT})), 0.01)$;

- **AST to Platelet Ratio Index (APRI) Calculation:**

APRI = $\text{round}(\text{AST}/\text{ASTULN} \times 100 / \text{platelet}, 0.1)$;

Note: for FIB-4 index and APRI calculation, the laboratory parameters need to be measured from the same blood draw. Age should be the actual age at the date when laboratory values are taken.

- **NAFLD fibrosis score (NFS) Calculation:**

NFS = $-1.675 + 0.037 \times \text{age}(\text{years}) + 0.094 \times \text{BMI}(\text{kg}/\text{m}^2) + 1.13 \times \text{IFG}(\text{impaired fasting glucose}) / \text{pre-diabetes or diabetes}(\text{yes} = 1, \text{no} = 0) + 0.99 \times \text{AST} / \text{ALT ratio} - 0.013 \times \text{platelet}(\times 10^9/\text{L}) - 0.66 \times \text{albumin}(\text{g}/\text{dL})$. Keep 3 decimal places.

The laboratory parameters need to be measured from the same blood draw. The last non-missing BMI on or prior to laboratory date should be used. Age should be the actual age at the date when laboratory values are taken. Status of pre-diabetes/diabetes should also be decided on the laboratory date. If a subject had pre-diabetes/diabetes at baseline, the pre-diabetic/diabetic status will be yes for all the postbaseline visits. If the subject does not have pre-diabetic/diabetes at baseline, the diabetic status will be determined based on the start date AEs of pre-diabetes and diabetes, and the collection date when fasting glucose is greater than 100 (IFG). If the AE start date or the fasting glucose collection date is on or prior to the laboratory date of a specific visit, then the diabetic/pre-diabetic status will be yes for that visit and later visits. If the day of the AE start date is missing, it will be imputed using the 1st day of the month.

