### 8.7. Assessment of Noninvasive Measures of Fibrosis

Receiver operating characteristic (ROC) curves and measures of diagnostic test performance (e.g., sensitivity and specificity) will be used to determine whether baseline noninvasive measures of fibrosis and their change from baseline can predict histological regression and progression of fibrosis or the development of clinical complications.

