7.2. Laboratory Evaluations

Laboratory data collected during the study will be analyzed and summarized using both quantitative and qualitative methods. Summaries of laboratory data will be provided for the (OL) Safety Analysis Set as appropriate and will include data collected up to the last dose of any study drug in the Randomized/OL Phase plus 30 days for subjects who have permanently discontinued study drug in the Randomized (and before the first dosing date in the OL Phase)/OL Phase. The analysis will be based on values reported in conventional units. When values are below the LOQ, they will be listed as such, and the closest imputed value will be used for the purpose of calculating summary statistics as specified in Section 3.7.

A by-subject listing for laboratory test results will be provided by subject ID number and visit in chronological order for hematology, serum chemistry, and coagulation separately. Values falling outside of the relevant reference range and/or having a severity grade of 1 or higher on the CTCAE severity grade as described in [Appendix 2](#) will be flagged in the data listings, as appropriate.

No formal statistical testing is planned.

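### In SAP Appendix 7, one fasting glucose above 100 permanently adds 1.13 points to the NAFLD Fibrosis Score of a subject without pre-diabetes or diabetes at baseline, so change from baseline in these subjects is pushed upward

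*SAP*

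**What the plan says.** SAP Appendix 7 builds NFS from age, BMI, the AST/ALT ratio, platelets, albumin and one yes/no indicator for impaired fasting glucose (IFG), pre-diabetes or diabetes. The indicator carries a weight of 1.13.

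The post-baseline rules for the indicator are:

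- **Positive at baseline:** "If a subject had pre-diabetes/diabetes at baseline, the pre-diabetic/diabetic status will be yes for all the postbaseline visits".
- **Negative at baseline:** status depends on the start dates of pre-diabetes or diabetes adverse events, and on "the collection date when fasting glucose is greater than 100 (IFG").
- **Timing and persistence:** it is enough that one such date falls no later than the day of the visit's blood sample. The SAP's consequence is: "then the diabetic/pre-diabetic status will be yes for that visit and later visits".

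No second value is asked for, and no rule returns the indicator to zero. The same paragraph requires the laboratory inputs to come from one blood draw, and says that pre-diabetes/diabetes status is to be settled as of the laboratory date.

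The threshold of 100 has no unit. SAP 7.2 says of the laboratory summaries "The analysis will be based on values reported in conventional units", so mg/dL is the natural reading.

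Glucose belongs to the chemistry panel (Protocol 6.11.1). That section requires fasting before all study visits, and Protocol Appendix 2 schedules chemistry at every clinic visit.

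**The concern.** A flag that can move only from no to yes, and is re-tested at every visit, fills up over time even if nobody's usual glucose changes. Carrying a diagnosis forward is sensible, because a diagnosis is a lasting state. One unconfirmed reading of 101 is not a diagnosis, yet under this rule a Week 8 reading still sets the score at Week 240.

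A higher NFS is read as more fibrosis. Subjects without pre-diabetes or diabetes at baseline would therefore appear to worsen on average with no change in the liver, and more so at later visits because more readings have been taken. Any analysis that uses post-baseline NFS, or its change from baseline, inherits this drift. Where NFS change is set against histology, the drift also blurs that relation.

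**Working it through.** The documents state no figure for this rule, so there is nothing to reproduce.

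**1. Size of the step (fixed by the documents).** With all other inputs held constant, switching the indicator changes NFS by 1.13. An example subject aged 55, with BMI 33, AST/ALT 0.9, platelets 210 and albumin 4.3, scores:

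−1.675 + 0.037×55 + 0.094×33 + 0.99×0.9 − 0.013×210 − 0.66×4.3 = −1.215

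The score is −0.085 with the indicator on. By the formula's own coefficients, 1.13 points equals:

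- 1.13/0.013 = 87 ×10⁹/L of platelets
- 1.13/0.037 = 30.5 years of age
- 1.13/0.094 = 12.0 kg/m² of BMI

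For comparison, true ageing over 240 weeks adds 0.037 × (240×7/365.25) = 0.17.

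**2. Persistence.** Give the same subject one glucose of 101 at Week 8 and values of 93 to 96 at every other visit.

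| Visit | Rule as written | Indicator judged at each visit |
|---|---|---|
| Week 8 | −0.079 | −0.079 |
| Week 12 | −0.076 | −1.206 |
| Week 48 | −0.051 | −1.181 |
| Week 240 | +0.085 | −1.045 |

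The 1.13 gap opened by one reading is still there at the end.

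**3. Number of readings.** The Protocol Synopsis schedules Weeks 1, 4, 8 and so on to 48, which is 13 post-baseline visits. It then has one visit every 12 weeks from Week 60 to Week 240, which is 16 more, or 29 in total. Unscheduled visits would add to this.

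**4. Group drift (assumption needed).** The documents give no glucose distribution. Let p be the chance that any one reading exceeds 100, independent across visits, in subjects negative at baseline. The share ever flagged after k readings is 1 − (1 − p)^k, and the gross mean rise is 1.13 times that share.

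| p (assumed) | Flagged by Week 48 | Flagged by Week 240 | Mean rise, Week 48 | Mean rise, Week 240 |
|---|---|---|---|---|
| 1% | 12% | 25% | +0.14 | +0.29 |
| 2% | 23% | 44% | +0.26 | +0.50 |
| 5% | 49% | 77% | +0.55 | +0.88 |
| 10% | 75% | 95% | +0.84 | +1.08 |

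**5. Excess over a same-draw rule.** Assume a usual glucose of 92 mg/dL and a within-subject SD of 6. Then p = P(Z > 8/6) = 0.091. By Week 48, 1 − 0.909^13 = 71% are flagged, a gross rise of 0.80. Judging the Week 48 draw alone flags 9%, worth 1.13×0.091 = 0.10. The excess is 0.80 − 0.10 = 0.70.

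If usual glucose also varies between subjects (mean 92, SD 6 between and within, with negative baseline status defined by two readings at or below 100), about 50% are flagged by Week 48 and 64% by Week 240. The Week 48 excess is then about 0.45.

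The result is sensitive to these assumptions. A usual glucose of 85 with SD 5 gives a Week 48 rise of only 0.02. A usual glucose of 95 with SD 6 gives 1.07.

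**The case against.** **Reach.** No readable text plans a between-arm comparison of post-baseline NFS. SAP 5.2 lists NFS as a baseline characteristic, where carry-forward does not operate. The exploratory endpoints and methods are blacked out. Protocol 8.7 plans to test whether "baseline noninvasive measures of fibrosis and their change from baseline can predict histological regression and progression of fibrosis", but does not name NFS, and SAP 6.5 moves that work to a separate plan. This stands and limits the weight of the point. Appendix 7 does write rules for post-baseline NFS, so such values are to be derived.

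**Stronger readings that do not hold.** A reader might infer any of the following:

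- *All non-diabetic subjects drift.* They do not. Subjects with pre-diabetes at baseline already carry the term, and a constant cancels in change from baseline.
- *A subject whose liver improves cannot show it.* Only the indicator is locked. AST/ALT, platelets, albumin and BMI still move the score.
- *The treatment comparison is biased.* The rule is identical in all arms. It would bias a difference only if glucose excursions, adverse events or length of follow-up differed by arm, and the documents show no such difference.

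**The rule as a choice.** Treating pre-diabetes or diabetes as a lasting state is recognisable, and SAP Appendix 3 does so for the Pooled Cohort score. But Appendix 3 carries diabetes forward from baseline status or an adverse event only, with no glucose trigger, so it supports the narrower rule.

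**Noise.** A same-draw indicator flips in subjects near 100. In the 92/6 example, the SD of the term under the rule as written is 1.13×√(0.71×0.29) = 0.51 at Week 48 and 1.13×√(0.94×0.06) = 0.27 at Week 240. Under the same-draw rule it is about 0.33 at both. The alternative is therefore noisier late in the study. That is a real cost, but a smaller one than a systematic one-way drift.

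**Conclusion.** The point holds for subjects without pre-diabetes or diabetes at baseline. In them the indicator can only move NFS change from baseline upward, and more subjects switch as readings accumulate.

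What is certain from the documents is the step of 1.13 per switched subject, the single-value trigger and the absence of a way back. The group size is not certain. The range of +0.14 to +0.84 at Week 48 rests on an assumed 1% to 10% chance per reading and independence between visits, and it applies only to subjects negative at baseline. Their share of each arm is unknown, so no arm-level figure can be given.

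Appendix 7 also does not define baseline pre-diabetes, or say whether a Screening or Day 1 glucose above 100 counts. This decides who can switch later and could move the drift either way.

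The effect is mainly on within-arm change, in a marker that is neither primary nor secondary. It is a minor-to-moderate point, worth correcting because the correction is cheap.

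**What to change.** In the NFS section of SAP Appendix 7:

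1. Carry status forward only for diagnosed pre-diabetes or diabetes, from baseline history or an adverse event.
2. Set glucose-based IFG at each visit from the fasting glucose in the same draw as the other NFS inputs: yes if above 100, otherwise no. Apply the same rule at baseline, which also settles whether a baseline glucose counts.
3. Print the unit.

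The cost is a sentence or two of SAP text and one derivation line, with no new data. The downside is that the term can flip between visits in subjects near 100.

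If that flipping is unwelcome, an alternative is a permanent flag only after two consecutive values above 100. At the assumed 1%, 5% and 10% per reading, this cuts the mean rise at Week 240 from 0.29, 0.88 and 1.08 to 0.003, 0.07 and 0.26. It reduces the drift but does not remove it.

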Appendix 8. SAS Program for Tipping Point Analysis for Binary Endpoint

The following **%tp_binary** macro generates multiple imputed data and a set of the shift parameters that adjust the imputed values will be examined.

```

/*-----*/
/*--- Delta-Adjusting Method for Tipping Point Analysis for Binary Endpoint ---*/
/*--- Generate imputed data set for specified shift parameters ---*/
/*--- data= input data set ---*/
/*--- smin= min shift parameter for active drug ---*/
/*--- smax= max shift parameter for active drug ---*/
/*--- sinc= increment of the shift parameter for active drug ---*/
/*--- trt= treatment group indicator ---*/
/*--- out= output imputed data set ---*/
/*-----*/

%macro tp_binary( data=, smin=, smax=, sinc=, trt=, out=);
  data &out;
  set _null_;
  run;

  /*----- # of shift values -----*/
  %let ncase= %sysevalf( (&smax-&smin)/&sinc, ceil );

  /*----- Imputed data for each shift -----*/
  %do jc=0 %to &ncase;
    %let sj= %sysevalf( &smin + &jc * &sinc);

    proc mi data=&data seed=20190000 nimpute=50 out=outmi;
      var trt01pn strat1V strat2V pe48;
      class trt01pn strat1V strat2V pe48;
      monotone logistic (pe48 / link=logit);
      mnar adjust( pe48(event='1') / adjustobs=(trt01pn="&trt") shift= &sj);
    run;

    data outmi;
    set outmi;
    Shift_Trts= &sj;
    run;

    data &out;
    set &out outmi;
    run;

  %end;
%end;
%mend tp_binary;

```

SAP GS-US-384-1943

ELECTRONIC SIGNATURES

Signed by	Meaning of Signature	Server Date (dd-MMM- yyyy hh:mm:ss)
PPD	Clinical eSigned	23-Jan-2019 21:31:31
PPD	Biostatistics eSigned	25-Jan-2019 02:05:16
